#### Treatment-Related AE

A treatment-related AE is any treatment-emergent adverse event that per investigator review has a reasonable possibility of being caused by the investigational product.

**Event with missing/unknown relationship to treatment will be assumed to be treatment-related.**

#### Dose Limiting Toxicities (DLT)

A DLT will be defined as any of the events described in protocol section 6.2.1.3 occurring in a subject during the DLT window. The DLT window will start on D1 (start of the administration of the first dose) and last for 28 days for all cohorts. Any adverse event occurring outside the DLT window that is determined by the investigator to be possibly related to the investigational product, which is seen more frequently or is more severe than expected or is persistent despite appropriate management, can be determined to be a DLT upon unanimous decision by the DLRT after review of the adverse event and all available safety data. Investigators will determine whether an adverse event qualifies as a DLT per protocol Section 6.2.1.3 and it will be collected by the flag indicating DLT in Events CRF.

Maximum Tolerated Dose (MTD)

The MTD is defined as the highest dose level whose DLT rate has the highest probability of the target TPI, an excessive/unacceptable TPI of < 0.25, and a minimum of 6 subjects have been treated at the MTD.

Overall Response (for R/R AML)

Overall response is defined as any of the following: complete remission (CR), CR with incomplete recovery (CRi), morphologic leukemia-free state, partial remission (all according to Revised International Working Group [IWG] response criteria) or CR with partial hematologic recovery (CRh).

Duration of Response (DOR) (for R/R AML)

Duration of response is defined as the number of days between the date of the first disease assessment indicating an overall response through the subsequent date of progression or relapse as defined by revised IWG response criteria or death due to any cause, or where applicable date of censoring [date of first progressive disease assessment or relapse or death or date of censoring – date of the first objective response result +1]. Subjects who respond and have not progressed or relapse or died while on study will be censored at the last adequate disease assessment date. Subjects who do not achieve an overall response will be excluded from the analysis of duration of response.

MRD Conversion Rate

MRD conversion rate is the number of subject achieve MRD- among subjects at who are MRD+ at enrollment. [REDACTED]

Overall Survival

Overall survival (OS) is defined as the time from the start of treatment (Study day 1) until event of death due to any cause.

OS time (Days) = Date of death – Study Day 1 + 1

OS time (Months) = (Date of death – Study Day 1 + 1)/30.4

Subjects still alive will be censored at the date last known to be alive. If the date last known to be alive is after the date that triggers the analysis (ie, the data cutoff date), the subject will be censored at the analysis trigger date.

Relapse-free Survival (RFS) (for MRD+ group)

RFS time will be calculated from the date of first administration of AMG 427 until the date of a hematologic relapse or death, whichever occurs first. Subjects still alive and relapse-free will be censored on their last disease assessment date.

## 6. Analysis Sets

The analysis of all endpoints, unless noted otherwise, will be conducted on the Safety Analysis Set.

### 6.1 Full Analysis Set

NA

### 6.2 Safety Analysis Set

All subjects that are enrolled and received at least 1 dose of AMG 427.

### 6.3 Per Protocol Set(s)

NA

### 6.4 Health-related Quality-of-Life or Health Economics Analyses Set(s)

NA

### 6.5 Pharmacokinetic/Pharmacodynamic Analyses Set(s)

The PK Analysis Set will contain all subjects who have received at least 1 dose of the investigational product and have at least 1 PK sample collected. These subjects will be evaluated for PK analysis unless the number of data points required for analysis is not enough, or significant protocol deviations have affected the data, or if key dosing or sampling information is missing.

### 6.6 Interim Analyses Set(s)

NA

### 6.7 Study-specific Analysis Sets

#### **Dose Limiting Toxicity (DLT) Evaluable Analysis Set:**

DLT Evaluable Analysis Set includes all DLT-evaluable subjects defined as all subjects who have received the doses planned for the respective cohort, and completed the DLT window of 28 days for all cohorts unless he/she drops out before completion of the DLT window for reasons other than a DLT; **exception:** if a subject has received the planned doses in cycle 1 and drops out within 1 week of the completion of the DLT period due to progressive disease, that subject will be considered DLT-evaluable and will not be replaced. The DLT window may also be extended to assess events starting within the window in case the DLT definition is time dependent. The analysis of DLT will be restricted to DLT Evaluable Analysis Set.

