3.1.3 Expansion Cohort

At completion of the dose escalation cohorts, approximately 90 additional subjects (approximately 40 R/R AML subjects in the FIH cohorts and 50 MRD+ AML subjects in the MRD+ cohorts) will be enrolled in dose expansion cohorts to gain further clinical experience, safety, and efficacy data in subjects with AMG 427. The dose to be evaluated will be at or below the MTD estimated in the dose escalation cohorts. Once the preliminary MTD and R2PD are established, the FDA will be provided with brief interim results of the dose escalation phase.

In the expansion phase, all available study data will be reviewed (with recruitment ongoing) by the DLRT once every 6th subject has at least completed their first treatment cycle plus 2 weeks or dropped out of treatment/study, whichever occurs earlier. The MTD will be further evaluated by applying BLRM using all available data, including data from subjects in the expansion phase. Ad hoc meetings may be convened any time in case of important safety events (see also Section 6.2.1.3).

Based on emerging safety data, the planned dose level and dose schedule may be modified during the conduct of the expansion phase. Additionally, enrollment to dose expansion will be paused and possibly terminated if safety stopping rules and/or efficacy futility rules are met (see Section 10.3 for details).

A final estimate of the MTD and RP2D using BLRM will be evaluated and confirmed utilizing all DLT-evaluable subjects from the dose escalation and the dose expansion cohorts. For definition of DLT-evaluable, see Section 6.2.1.3. Additional expansion cohorts testing alternative dose levels or biologic subsets may be considered by amendment.

The overall study design is described by a [Study Design and Treatment Schema](#) at the end of the protocol synopsis section.

The study endpoints are defined in Section 10.1.1.

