6.2.1.3 Dose-cohort Study Escalation and Stopping Rules, Dose Limiting Toxicities (DLTs)

A DLT will be defined as any of the events described below occurring in a subject during the DLT window. The DLT window will start on D1 (start of the administration of the first dose) and last for 28 days for all cohorts. Any adverse event occurring outside the DLT window that is determined by the investigator to be possibly related to the investigational product, which is seen more frequently or is more severe than expected or is persistent despite appropriate management, can be determined to be a DLT upon unanimous

recommendation by the DLRT after review of the adverse event and all available safety data.

DLT Evaluation

A subject will be DLT-evaluable if the subject has received the doses planned for the respective cohort, and completed the DLT window of 28 days for all cohorts. The DLT window may also be extended to assess events starting within the window in case the DLT definition is time dependent (eg, in case of neutropenia).

A subject is not DLT-evaluable if he/she drops out before completion of the DLT window for reasons other than a DLT; exception: if a subject has received the planned doses in cycle 1 and drops out within 1 week of the completion of the DLT period due to progressive disease, that subject will be considered DLT-evaluable and will not be replaced. All available safety data for subjects who are not DLT evaluable will still be evaluated and considered in DLRM recommendations. A DLT will be defined as any of the events described below occurring in a subject during the DLT window unless clearly attributable to causes other than AMG 427 treatment. The CTCAE version 4.0 (see [Appendix A](#)) will be used to assess toxicities/adverse events with the exception of CRS (see [Table 6](#) for grading criteria of CRS) and **immune-effector associated neurotoxicity syndrome (ICANS)** (see [Table 8](#) for grading criteria of ICANS).

Events to be considered as DLTs and exceptions are listed below:

- Cases of drug-induced liver injury confirmed by Hy's Law criteria
- Any treatment-related death
- Grade 2 or 3 CRS meeting any of the criteria listed below:
 - Grade 2 CRS that does not resolve, with or without intervention, to \leq grade 1 within 7 days will be considered a DLT
 - Grade 3 CRS that does not resolve, with or without intervention, to \leq grade 2 within 5 days, or \leq grade 1 within 7 days, will be considered a DLT

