 - Grade 3 CRS reported at the initial run-in dose (ie, at MTD1; applicable only after MTD1 has been defined) will be considered a DLT
 - Two separate events of grade 3 CRS
- Grade 4 CRS/infusion reactions occurring during AMG 427 treatment, immediately stop the infusion. Permanently discontinue AMG 427 therapy.
- Grade 3–5 non-hematologic toxicity not clearly resulting from the underlying leukemia EXCEPT:
 - alopecia
 - grade 3 rash
 - grade 3 fatigue, asthenia, fever, anorexia, or constipation

- grade 3 nausea, vomiting or diarrhea not requiring tube feeding, total parenteral nutrition, or requiring or prolonging hospitalization
- infection, bleeding, or other expected direct complication of cytopenias due to active underlying leukemia
- grade 3 infusion reaction including CRS, if successfully managed and which resolves within 12 hours
- grade 3 TLS if it is successfully managed clinically and resolves within 7 days without end-organ damage.
- Grade 4 neutropenia that persists beyond 42 days in the absence of leukemia
- Laboratory parameters \geq grade 3, not considered clinically relevant, and improved to \leq grade 2 within 72 hours, will not be considered DLT's. Laboratory parameters with long half-lives, ie, ALT, GGT, ALP, and lipase, will likewise not be considered DLT's if they are not considered clinically relevant, and improve to grade \leq 2 within 7 days.
- Grade 3 transaminitis (per CTCAE criteria) reported for subjects with grade 2 CRS (per Lee et al, 2019 criteria) will not be reported as a DLT if there is improvement to CRS \leq grade 1 within 7 days.

The dosing schedule is described by a schema in [Figure 2](#).

See Section [3.1](#) for description of dose escalation and stopping rules and Section [3.4](#) for description of replacement of subjects.

Subjects who have experienced a DLT at a certain dose level may continue to receive AMG427 at a lower dose, if AMG 427 has shown a potential for benefit in the specified subject, the subject's adverse events have reduced to grade 2 or lower, and after discussion with the Amgen Medical Monitor.

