If possible, the number of infusions at the target dose in a cycle should sum up to the planned number of infusions. In this case, the cycle would still be DLT-evaluable.

Permanent Discontinuation

A subject will permanently discontinue treatment with investigational product in the event of:

- dose-limiting or other unmanageable toxicity
 - except subjects who have experienced a DLT at a certain dose level may continue to receive AMG427 at a lower dose, if AMG 427 has shown efficacy in the specified subject, and the subject's adverse events have reduced to grade 2 or lower, and after discussion with the Amgen Medical Monitor.
- grade 4 CRS
- grade 2 or 3 CRS meeting any of the criteria listed below:

- grade 2 or 3 CRS that does not improve to \leq grade 1 within 7 days
- grade 3 CRS that does not improve to \leq grade 2 within 5 days
- grade 3 CRS at the initial run-in dose for a cycle (ie, at the MTD1) (for cohorts with dose step only)
- If a subject experiences 2 separate grade 3 CRS events
- disease progression as defined by revised IWG response criteria ([Appendix E](#))
- withdrawal of subject's consent to treatment
- subject or investigator not compliant with the study protocol
- occurrence or progression of a medical condition, which in the opinion of the investigator, should preclude further participation of the subject in the study
- a treatment interruption of more than 21 days due to an adverse event not clearly related to the underlying disease (except neutropenia)
- occurrence of a CNS-related adverse event considered related to AMG 427 by the investigator and meeting 1 or more of the following criteria:
 - more than 1 seizure
 - a CNS-related adverse event grade 4
 - a CNS-related adverse event leading to treatment interruption that needed more than 1 week to resolve to grade \leq 1
- graft-versus-host disease
- investigator's decision that a change of therapy (including immediate HSCT) is in the subject's best interest

Females who become pregnant while on study through 4 weeks after receiving the last dose of study drug will not receive subsequent scheduled doses and will be followed for safety until the end of study visit.

Males on study through 4 weeks after receiving the last dose of study drug must practice sexual abstinence or use a condom while on study through 4 weeks after receiving the last dose of study drug.

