Cytokine release is an anticipated consequence of T cell engagement induced by AMG 427. Cytokine release syndrome, including serious events **and a fatal event**, has been reported **in subjects** receiving AMG 427 in the clinical trial. Subjects may be at an increased risk for CRS during the first few days following the initial dose of AMG 427 and after a dose step. **More severe cases of CRS and/or ICANS have also been associated with higher tumor burden in multiple malignancies including leukemia, lymphoma, and multiple myeloma, which is likely to be associated with greater expansion of T cell populations and synchronous activation with BiTEs. Please refer to the Investigator’s Brochure for additional information.**

Infusion reactions may be clinically indistinguishable from manifestations of CRS. Throughout the infusion with AMG 427 and at least **12** hours after the start of infusion, monitor subjects intensively for clinical signs (eg, fever, hypotension, tachycardia, dyspnea, tremors) and laboratory changes (eg, increase **in transaminases, C-reactive protein [CRP], lactate dehydrogenase [LDH], ferritin, D-dimer, and erythrocyte sedimentation rate [ESR]**) which may be related to CRS. Cytokine release syndrome may be clinically associated with the development of fever, nausea, chills, hypotension, tachycardia, asthenia, headache, rash, scratchy throat, dyspnea, **and ICANS/neurotoxicity** as a consequence of systemic release of cellular cytokines such as TNF, **IL-1Ra**, IL-2, IL-3, IL-4, and IL-6 (**Morris et al, 2021; Winkler et al, 1999**). Potentially life-threatening complications of CRS include cardiac dysfunction, adult respiratory distress syndrome, renal and/or hepatic failure, and disseminated

intravascular coagulation (Lee et al, 2014) and **ICANS/neurotoxicity which may occur concurrently or immediately following CRS.**

Grading of CRS should be performed according to the guidelines provided in **Table 6** and management of CRS should be performed according to the guidelines provided in **Table 7** (based on the adopted grading system referenced in Lee et al, 2019).

Table 6. Cytokine Release Syndrome Grading (ASTCT; Lee et al, 2019)

CRS Parameter	Grade 1	Grade 2	Grade 3	Grade 4
Fever ^a	Temperature $\geq 38^{\circ}\text{C}$	Temperature $\geq 38^{\circ}\text{C}$	Temperature $\geq 38^{\circ}\text{C}$	Temperature $\geq 38^{\circ}\text{C}$
		With		

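### As worded, the SAP's DLT Evaluable Analysis Set omits a subject whose DLT ends dosing, or reduces it without make-up, before the last planned dose; the intent is to count such subjects, and the text should say so

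*SAP*

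**What the plan says.** **SAP Section 6.7** defines the set as "all subjects who have received the doses planned for the respective cohort, and completed the DLT window of 28 days". A further clause takes out subjects who leave before the window ends for some cause other than a DLT. One exception keeps subjects who leave for progressive disease in the last week of the window, and it too requires the planned doses. The section then restricts the DLT analysis to this set.

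**Protocol Section 6.2.1.3** uses two separate sentences. The first reads "A subject will be DLT-evaluable if the subject has received the doses planned for the respective cohort" and adds completion of the 28-day window. The second reads "A subject is not DLT-evaluable if he/she drops out before completion of the DLT window for reasons other than a DLT". A safeguard follows: "All available safety data for subjects who are not DLT evaluable will still be evaluated and considered in DLRM recommendations".

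**What happens after a DLT.** Protocol Section 6.2.1.4 lists "dose-limiting or other unmanageable toxicity" among the grounds for permanent discontinuation. The alternative, under conditions, is in Section 6.2.1.3: "Subjects who have experienced a DLT at a certain dose level may continue to receive AMG427 at a lower dose". Section 6.2.1.4 also keeps a cycle evaluable when, where possible, the infusions at the target dose are brought up to the planned number.

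**What depends on the set.** Protocol Section 10.1.2 limits the DLT analysis to evaluable subjects. SAP Section 3.1 (Expansion Cohort) bases the final MTD and RP2D on them. SAP Section 9.6.1 fits the BLRM to DLT incidence. Protocol Section 3.4 replaces non-evaluable subjects during escalation.

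**The concern.** An analysis set is programmed from its definition. Here the first condition, receipt of the planned doses, can fail because of the very event the set exists to count. A treatment-related death is a DLT. Grade 4 CRS appears in the DLT list together with permanent discontinuation. If either occurs before the last planned dose (day 8 or day 19 in Schedule C), the planned doses are never received, and the SAP wording puts the subject outside the set.

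Such a subject is lost from both numerator and denominator. Treated in escalation as non-evaluable, the subject would also be replaced. The DLT rate would then be too low in the primary DLT summary, in a BLRM fitted to this set and in the final MTD estimate, and the DLTs most liable to be lost include the gravest early ones. Early DLTs are plausible: protocol Section 6.6 says "Subjects may be at an increased risk for CRS during the first few days following the initial dose of AMG 427", and adds the period after a dose step.

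**Working it through.** **1. Reading SAP Section 6.7 clause by clause**

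Take a subject with a DLT after the first dose who stops AMG 427 permanently.

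- Planned doses received: no.
- 28-day window completed: possibly, if the subject stays under observation; no, if the subject dies.
- Clause on dropping out: it only takes subjects out. Someone who has completed the window cannot have left before its end, so, read literally, the clause removes nobody whom the window condition has not already removed. The likely purpose was to waive window completion for DLT drop-outs. Even read that way, it does not waive the planned doses.
- Exception: progressive disease only, with planned doses received.

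Result: not in the set.

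For a subject who continues at a lower dose, the answer depends on protocol Section 6.2.1.4. If target-dose infusions reach the planned number, the cycle stays evaluable; if not, the subject is excluded.

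**2. Comparison with the protocol**

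The second protocol sentence confines the non-evaluable class to drop-out for other reasons. A DLT drop-out is not in that class, so the intent is to count such subjects. The first sentence gives a condition under which a subject is evaluable; it need not be the only one. The protocol therefore leaves DLT drop-outs unclassified. The SAP's form of words turns the same conditions into requirements. SAP Section 10 reports no changes from the protocol's analyses, so the tightening does not look deliberate.

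**3. Illustration with the expansion pause rule**

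Inputs from SAP Section 3.3: prior Beta(0.40, 1.60); pause if P(DLT rate > 0.20) > 0.80; looks every 6 subjects; boundaries in SAP Table 1. With r DLTs in n subjects the posterior is Beta(0.4 + r, 1.6 + n − r).

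Reproduction: the smallest r that passes 0.80 matches all 8 boundaries. Exact binomial recursion over the looks, with N = 40 and N = 50, matches every row of SAP Table 2. At a true rate of 0.30 it gives early stopping of 78.9% (R/R) and 85.5% (MRD+).

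Then remove one DLT subject from a count that is exactly at the boundary:

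| At boundary | P(rate > 0.20) | One DLT subject removed | P(rate > 0.20) |
|---|---|---|---|
| 3/6 | 0.914 | 2/5 | 0.778 |
| 4/12 | 0.821 | 3/11 | 0.664 |
| 6/18 | 0.883 | 5/17 | 0.786 |
| 7/24 | 0.831 | 6/23 | 0.724 |
| 9/30 | 0.885 | 8/29 | 0.811 |
| 10/36 | 0.848 | 9/35 | 0.767 |
| 11/42 | 0.812 | 10/41 | 0.727 |
| 13/48 | 0.865 | 12/47 | 0.80004 |

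The pause is lost at 6 of the 8 looks. It survives at n = 30 and, barely, at n = 48.

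**4. Effect on stopping probability, with assumed loss**

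Let f be the share of DLT subjects excluded. The documents give no value, so f is an assumption. The apparent rate among counted subjects is p(1 − f)/(1 − pf). At p = 0.30:

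- f = 0.10: 0.27/0.97 = 0.278; early stopping 70.8% (R/R) and 77.9% (MRD+).
- f = 0.25: 0.225/0.925 = 0.243; early stopping 54.9% and 61.4%.

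The corresponding effect on the BLRM cannot be computed here, because the dose levels and the doses that anchor the prior are blacked out.

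**The case against.** The strongest reply is that the intent is plain and the safeguards are real. The protocol names only drop-out for other causes as non-evaluable, so it does not clearly send a DLT subject to replacement under Section 3.4. Protocol Section 6.2.1.3 keeps the safety data of non-evaluable subjects in DLRM recommendations, and SAP Section 7.1 brings DLTs in all subjects into every enrollment and dosing decision. This stands, and it limits the effect on dosing decisions during the trial. It does not settle who enters the DLT table or the final MTD estimate.

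Other objections narrow the point, and each is accepted:

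- Reduced dosing does not by itself exclude a subject, because made-up cycles remain evaluable. That provision cannot help after death or permanent discontinuation.
- Protocol Section 6.6 speaks of a possible increase in CRS risk, both early and after a dose step, and a dose step may fall on day 8, 12 or 19. It makes early DLTs plausible; it does not show that most DLTs precede the last dose.
- The expansion review trigger in protocol Section 3.1.3, which includes subjects who "dropped out of treatment/study, whichever occurs earlier", concerns the timing of DLRT review and is no evidence about evaluability.
- SAP Table 1 counts only a number of subjects and ends at the planned enrollment of 40 and 50. Its link to the evaluable set is an inference from Section 6.7.

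**Conclusion.** The point holds as a defect in the wording of SAP Section 6.7, with a smaller gap in protocol Section 6.2.1.3. Applied literally, the SAP rule understates the DLT rate. Under the evident intent there is no understatement, and none arises for a DLT subject who received all planned doses and completed the window.

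A reader might infer that the sponsor chose to leave DLT subjects out, that both documents exclude them, or that the printed operating characteristics are wrong. The documents support none of these. The protocol's second sentence points the other way, its first can be read as sufficient only, and SAP Table 2 is correct when every DLT is counted.

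The true size is unknown. The change from 0.914 to 0.778 assumes that the pause rule counts this set and that the count sits exactly at the boundary. The stopping probabilities also rest on assumed loss shares of 10% and 25%. All are illustrations of direction, not estimates. Because the set carries the primary DLT endpoint and the MTD in a first-in-human trial, the wording should be corrected.

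**What to change.** In SAP Section 6.7, and for consistency in protocol Section 6.2.1.3, define a DLT-evaluable subject as one who received at least 1 dose of AMG 427 and either:

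- (a) had a DLT within the DLT window, including its stated extension, regardless of doses received or window completed; or
- (b) had no DLT, received the planned doses (counting infusions made up under protocol Section 6.2.1.4) and completed the window, with the present progressive-disease exception kept.

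Limb (a) should stop at the window. Events outside it that the DLRT declares to be DLTs stay under the existing rule; admitting them whatever the dosing would go beyond this defect and could push the rate upward. In SAP Section 3.3, state which set the expansion pause rule counts.

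The cost is one reworded definition in each document and one sentence in SAP Section 3.3. No new data are needed, since DLTs are already flagged on the Events CRF (SAP Section 5). The wording also settles that a subject with a DLT in the window is not replaced as non-evaluable. No dosing or discontinuation rule changes.
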